At the second study call, participants ($N=608$) will be randomized to one level of each of 4 factors (see Table 2): 1) Medication Type (Varenicline vs. C-NRT), 2) Preparation Medication (4 weeks vs. Standard), 3) Medication Duration (Extended vs. Standard), and 4) Counseling (Intensive vs. Minimal). Participants will complete phone assessments one week pre-quit, during the first week post-target quit date (TQD) and at Weeks 2, 4, 12, 20, 26, and 52 post-TQD.

Assessments

Call 1. At Call 1, participants will complete the phone screen, complete the oral consent and HIPAA authorization process, and complete a brief demographics assessment. After this call, participants will be mailed a Study Information Sheet that contains all of the information related to the study. They will also be sent information on how to use WebEx so they can have video visits if they so choose.

Call 2. Participants will answer questions about their smoking and other tobacco use history, their self-efficacy and motivation, their physical and emotional health, the impact of Covid-19 on their life and their beliefs about Covid-19 and smoking, and their satisfaction with their health care and they will complete the Fagerström Test of Cigarette Dependence¹¹⁷ (see Table 1). Participants will be randomized to their treatment condition, set a target quit date, and be educated about their assigned medication (including how and when to request refills).

Calls 3-6. Participants will receive a call one week pre-quit, during the first week post-target quit date (TQD) and at Weeks 2 and 4 from their Health Counselor. This research staff member will assess: a daily smoking calendar using timeline follow-back¹¹⁸, medication use (as appropriate

PROTOCOL
 "P01 Cessation Screening Study"
 PI: [name].; UW-CTRI Grant:

based on study condition), use of alternative nicotine products (e.g., e-cigarettes), withdrawal, self-efficacy, and adverse events. We will recommend dosage/use alterations as per good clinical practice if participants experience adverse events. Participants will be referred to their primary care physician should they require medical consultation. Participants will also receive smoking cessation counseling as appropriate, based on their assigned treatment condition. If the call does not include treatment it will not be conducted by the participant's health counselor (i.e., Calls 5 and 6 for those in the Minimal Counseling condition).

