Participants will be told their treatment condition at Call 2, set a target quit date (TQD), and instructed how to use their study medications. Medications will be mailed following this call, along with a handout that describes: 1) when to begin taking study medication; 2) the type and doses involved; 3) how and when to obtain the next month's medication; and 4) complete instructions on proper medication use, including information from the package insert and contact information if they have questions regarding their medication and/or symptoms they experience. Participants will be mailed all Preparation Medication as well as one month of post-quit study medication after Call 2. They will need to call in to a study line to request that more medication be mailed to them (Standard Duration participants will call one time to receive their final 2 months of medication; Extended Duration participants will call once to get 2 additional months of medication and again to get the remaining 3 months of study medication). Participants will also receive a counseling handout with their medications; those randomized to intensive counseling will receive a Quit Plan listing their target quit day and when they start the medications and those randomized to minimal counseling will receive the mHealth handout.

Medication Type: Varenicline vs. C-NRT. Half of participants will be assigned to receive varenicline and half to receive nicotine patch + mini-lozenge (C-NRT). Unless participants are assigned to Preparation or Extended Duration, they will receive the standard dosing and duration of pharmacotherapy (e.g., 12 weeks of varenicline starting 1 week prequit or 12 weeks of C-NRT starting on the TQD; see Table 2).

Preparation

Medication: 4 weeks vs. Standard. Half of participants will be assigned to receive the Preparation Medication ("ON" condition); they will be instructed to use their assigned medication type (varenicline or nicotine patch) for 4 weeks prior to their TQD (see Table 2). Participants will use a lower dose of NRT (14-mg patches) while they are still smoking to reduce the risk of adverse events. Our prior research found no significant increases in adverse events among smokers who used NRT prior to the TQD and prior research has shown that use of

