The other half of the participants receive a brief (15-30 minute) phone/video counseling session 1 week prior to the TQD to promote engagement with free mobile health (mHealth) resources: smokefree.gov and/or the Wisconsin Tobacco Quit Line, mHealth resources developed and maintained by the National Cancer Institute and the Wisconsin Department of Health Services. This will include a fax referral to the Wisconsin Tobacco Quit Line, which will then fax back to the research office what services the participant received (i.e., did they complete the counseling call, were they sent any smoking cessation medications). Smokefree.gov allows participants to develop a quit plan and access different quit smoking resources. The Quit Line is an interactive program that involves one-on-one telephone coaching sessions with a trained Quit Line coach to encourage smoking cessation, offer personalized advice on how to quit, information on medications, and assistance with choosing a quit date and creating a plan. This counseling will include informing participants about the features of the resources and encouraging them to sign up during their counseling session and a mailing that describes the mHealth resources. Participants will then receive a brief (10-20 minute) follow-up phone/video session during the first week post-TQD to mimic a nurse or clinician follow-up after a quit attempt and to provide additional mentoring around the use of the mHealth resources (e.g., has the participant signed up/used these resources, recommendation for specific pages that would be appropriate).

All participants will receive the medication conditions as outlined above, regardless of their counseling condition. Regular team meetings will discuss safety, confidentiality, and fidelity to the counseling manual. Health counselors (HCs) will also meet for 2 hours/month for clinical supervision with the Project Leader, [name], a licensed clinical psychologist, to review the study protocol and address treatment issues.

Promoting Continued Experimental Participation

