Additional Analyses. We will examine the main and interactive effects of the 4 factors on the occurrence of adverse events and treatment engagement (count and proportion of counseling sessions completed [1 session for Minimal vs. 4 sessions for Intensive], counseling modality [video vs. phone] chosen for remote protocol participants, count and proportion of medication refills requested [1 for Standard Duration vs. 3 for Extended duration]). Logistic and linear regression will be used for categorical and continuous variables, respectively, with appropriate transformations of continuous variables and/or adoption of generalized regression modeling techniques as necessary. The primary analyses will be unadjusted and then we will statistically control for covariates including: living with a smoker, biological sex, age, clinic, health system, use of other tobacco products at baseline, cigarettes per day at baseline, and education. Analyses of these exploratory outcomes will achieve scientific rigor by controlling for experiment-wise error in families of related tests using the Benjamini-Hochberg approach.

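### The SAP's engagement measures list 1 Minimal counseling session and 3 Extended refills, but the protocol schedules 2 of each, so the exploratory Counseling and Duration comparisons may be mis-scaled

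*SAP*

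**What the plan says.** The SAP, under Additional Analyses, plans main and interactive effects of the four factors on treatment engagement. Two of the measures carry a number for each factor level: "count and proportion of counseling sessions completed [1 session for Minimal vs. 4 sessions for Intensive" and "count and proportion of medication refills requested [1 for Standard Duration vs. 3 for Extended duration". The section calls these outcomes exploratory and applies Benjamini-Hochberg control within families of tests.

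The protocol describes the same contacts differently.

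- **Minimal counseling** (Counseling: Intensive vs. Minimal): "The other half of the participants receive a brief (15-30 minute) phone/video counseling session 1 week prior to the TQD", and then "Participants will then receive a brief (10-20 minute) follow-up phone/video session during the first week post-TQD". Table 1 marks Minimal counseling at C3 and C4. Under Calls 3-6, the only calls named as carrying no treatment are "Calls 5 and 6 for those in the Minimal Counseling condition".
- **Refills** (Interventions): "Standard Duration participants will call one time to receive their final 2 months of medication", whereas "Extended Duration participants will call once to get 2 additional months of medication and again to get the remaining 3 months of study medication". Nothing has to be requested for the first supply: "Participants will be mailed all Preparation Medication as well as one month of post-quit study medication after Call 2".

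The two documents agree on four Intensive sessions and one Standard refill request.

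**The concern.** Two of the four numbers attached to the engagement measures do not match the intervention schedule. Each wrong-looking number belongs to one level of the factor being tested: Minimal within Counseling, and Extended within Duration. If these numbers serve as denominators, the mis-scaling coincides with the treatment contrast. It would then appear as a Counseling effect on attendance proportion or a Duration effect on refill proportion. Multiplicity control does not help, because the problem is bias and not chance.

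The reach is limited. The abstinence outcomes do not use these proportions, and neither do the two optimization criteria in the SAP (12-month abstinence and cost). Raw counts do not depend on a denominator. Attendance at counseling is also listed as a candidate mediator under Secondary Aims Analyses, but it is affected only if it is scored the same way.

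**Working it through.** **Step 1. Count scheduled contacts from the protocol and compare with the SAP.**

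| Level | Protocol | SAP | Score at full engagement (protocol / SAP) |
|---|---|---|---|
| Minimal sessions | 2 (C3, C4) | 1 | 2/1 = 200%, or 100% if capped |
| Intensive sessions | 4 (C3 to C6) | 4 | 4/4 = 100% |
| Standard refill requests | 1 | 1 | 1/1 = 100% |
| Extended refill requests | 2 | 3 | 2/3 = 67% |

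The protocol's supply adds up. Standard is 1 + 2 = 3 months with one request. Extended is 1 + 2 + 3 = 6 months with two requests. Preparation Medication adds no request.

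**Step 2. See whether another counting rule gives the SAP's refill pair (Standard 1, Extended 3).**

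- Requests: 1 and 2.
- Mailings, including the first: 2 and 3.
- Months supplied after the first: 2 and 5.

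None of these rules, applied to the protocol's schedule, gives 1 and 3.

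**Step 3. Size of the refill artefact.** Assume SAP denominators, delivery per protocol, and the same request rate p for every scheduled request. The documents give no value for p.

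- Standard: p/1 = p. Extended: 2p/3.
- Gap: p − 2p/3 = p/3.
- p = 0.5: 17 points. p = 0.7: 23 points. p = 1.0: 33 points.

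**Step 4. Size of the session artefact.** Assume an equal, independent attendance rate p at each session. The result depends on a scoring rule that the SAP does not state.

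- *Capped at 100%.* Minimal scores 100% if either session is attended, so its mean is 1 − (1 − p)² = 2p − p². Intensive has mean p. Gap: p(1 − p), which is 25 points at p = 0.5, 21 at 0.7, 9 at 0.9 and 0 at 1.0.
- *Only the first session counted.* Both means are p, so the gap is 0, but the second Minimal session goes unscored.
- *Both counted, uncapped.* Minimal has mean 2p, so the gap is p and individual scores can reach 200%.

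**Step 5. Is this visible against sampling error?** This is an illustration only, at p = 0.7 with (538 − 42)/2 = 248 per level. The even split is assumed. So is the 42-person exclusion, which the SAP states for the main outcome analyses and does not repeat for these.

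- Refills: variance 0.7 × 0.3 = 0.21 for Standard and (4/9)(0.21/2) = 0.0467 for Extended. SE = √[(0.21 + 0.0467)/248] = 0.032. The gap of 0.233 is about 7 SE.
- Sessions, capped: variance 0.91 × 0.09 = 0.0819 for Minimal and 0.21/4 = 0.0525 for Intensive. SE = √[(0.0819 + 0.0525)/248] = 0.023. The gap of 0.21 is about 9 SE.

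Under these assumptions, denominators of 2 (Minimal) and 2 (Extended) give expected gaps of 0.

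**The case against.** The strongest reply accepts the mismatch and disputes its weight.

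1. *The SAP never calls the numbers denominators, and nothing shows that delivery followed the protocol.* This stands, and every size above is conditional on both. It does not settle the conflict, because an analyst must still choose a denominator for the planned proportion.

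2. *The SAP may record what was actually delivered.* Mailings of at most two months after the first would need one request for Standard (2) and three for Extended (2 + 2 + 1), which is the SAP's pair. Neither document states such a schedule. The SAP's section on implementation challenges reports changes to medication supply, randomization, biochemical verification and sample size, but none to sessions or refills. Nor is the protocol simply an early text: it already has saliva cotinine, which the SAP dates to September 2023. If delivery did differ, the artefact disappears and the protocol needs correcting.

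3. *The second Minimal contact is a follow-up, so scoring one session is defensible.* As an operational choice it could be, and the average gap is then 0. But the protocol calls the contact a session, Table 1 lists it as counseling, and the refill conflict would remain.

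4. *Refill requests are sequential, so equal p is a poor model.* This is fair. If the second request can follow only the first, with conditional rate p, Extended participants make p(1 + p) requests on average. A denominator of 2 then leaves a gap of p − p(1 + p)/2 = p(1 − p)/2: 12.5 points at p = 0.5 and 10.5 at 0.7. That is a real difference in engagement. The part caused by using 3 in place of 2 is p(1 + p)/2 − p(1 + p)/3 = p(1 + p)/6: 12.5 and 19.8 points, against 17 and 23 under equal p. Falling attendance at the later Intensive sessions would likewise leave a genuine gap. Correct denominators remove the scaling error, but they need not make the observed gap zero.

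5. *The outcomes are exploratory, and 200% would be noticed.* Both are true. A 67% ceiling for Extended, or Minimal scores capped at 100%, would not stand out in the same way.

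**Conclusion.** The inconsistency is real: the SAP and the protocol disagree on two of the four per-level numbers, and the SAP gives no rule for the numerator, denominator or cap. The planned proportions cannot be derived reproducibly from the documents as written.

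If the SAP numbers are denominators and delivery followed the protocol, Extended cannot exceed 67% while Standard can reach 100%. With equal per-contact rates between 0.5 and 1.0, the spurious refill gap is 17 to 33 points. The spurious session gap runs from 25 points down to 0 if scores are capped. The rates are assumed, and the session figures also assume independent attendance. The standard-error comparison is only illustrative.

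The consequence is confined to exploratory engagement outcomes, and possibly the attendance mediator. It should be corrected before those analyses are run, but it does not touch the primary conclusion on abstinence.

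**What to change.** Reconcile the SAP's Additional Analyses with the protocol's Interventions section, Calls 3-6 text and Table 1, and establish from study records which sessions and refill requests were actually scheduled. Then:

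- State the numerator and denominator for each level in the SAP. The protocol as written implies 2 Minimal and 4 Intensive sessions, and 1 Standard and 2 Extended requests. If delivery differed, correct the protocol text and Table 1 instead.
- State whether the Minimal follow-up counts as a session, and whether scores are capped.
- Compare levels on the proportion of scheduled opportunities taken up. Report raw counts with a note that their maxima differ by design.
- Say whether the attendance mediator uses the same definition.

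The cost is a line of SAP wording or a protocol correction, and re-derivation of two exploratory variables. No new data are needed.
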